3.2.8 Study design

A stepped-wedge cluster randomized trial design will be used to evaluate the impact of the intervention. Using this design, the intervention will be implemented sequentially to the participating hospitals over 6-month time periods (Table 2). The period at which a hospital begins implementation of the intervention (or enters the “active phase” of the study) will be determined at random. The intervention will be applied at the level of the hospital (clusters). Participating hospitals will be randomized to one of four wedges, giving around 24 hospitals per wedge. Wedge

randomization will be computer-generated. The survivors will be followed up at 6 months and 12 months.

Table 2 Patient Selection and Intervention Plan

	0-6 month	7-12 month	13-18 month	19-24 month	25-30 month
A group (24 hospitals)	A0 (baseline)	A1 (intervention)	A2 (intervention)	A3 (intervention)	A4 (intervention)
B group (24 hospitals)	B0 (baseline)	B1 (baseline)	B2 (intervention)	B3 (intervention)	B4 (intervention)
C group (24 hospitals)	C0 (baseline)	C1 (baseline)	C2 (baseline)	C3 (intervention)	C4 (intervention)
D group (24 hospitals)	D0 (baseline)	D1 (baseline)	D2 (baseline)	D3 (baseline)	D4 (intervention)

3.2.9 Outcomes

The primary outcome will be the incidence rate of in-hospital major adverse cardiovascular events (MACE) comprising all-cause mortality, myocardial infarction or re-infarction and stroke. Secondary outcomes will be the key performance indicators (KPIs) and the patient satisfaction.

3.2.10 Sample Size

Sample size calculations are based on following assumptions:

- The baseline incidence rate of in-hospital major adverse cardiovascular events (MACE) is assumed as 8.4%. This parameter came previous findings from CPACS-1 (8.4%) and CPACS-2 studies (7.6%). Taking into account that participating hospitals in CPACS-3 come from remote areas with limited medical resources, a higher incidence of MACE in CPACS-1 is used to calculate the sample size;
- no delay in the effect of the intervention;
- an intra-class correlation coefficient of 0.10 (data from CPACS-2 study);
- 96 participating hospitals, 50 patients will be collected in each 6-month cycle in each hospital, and the intervention will be started in four steps;
- We select 4 hospitals from each province in Jiangsu Province, Guangdong Province, Gansu Province, Sichuan Province, Guizhou Province, and Inner Mongolia Autonomous Region and select 8 hospitals from each of the

remaining 9 provinces: Hebei Province, Liaoning Province, Jilin Province, Anhui Province, Shandong Province, Shanxi Province, Henan Province, Hubei Province, and Shaanxi Province.

This study will have 99%, 98% and 85% power to detect relative risk reduction of 25%, 20% and 15% respectively in the primary outcome (Table 3).

Table 3 Statistical power of CPACS-3

Relatively risk decline	Statistical power
25%	99%
20%	98%
15%	85%

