4.1 Effectiveness evaluation

For the primary end point (binary variable, in hospital major adverse cardiovascular events (MACE), including stroke, AMI, hospital readmission, vascular reconstruction and all-cause mortality), GLMM model will be used to evaluate the treatment effect (between intervention groups) and the time effect (between different patients in different time periods), with LOGIT/POSSION conversion of the end point. If there is neither the time effect nor the interaction term between time and intervention, the COX model or LOGISTIC regression model will be used to estimate the intervention effect after adjustment of covariates.

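### Table 3's 99/98/85% power does not follow from the inputs in section 3.2.10, which give about 95/82/57% with a constant ICC and less if hospital correlation decays between cycles

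*Protocol*

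**What the plan says.** Protocol section 3.2.10 lists the assumptions behind the power statement:

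- Control rate: "The baseline incidence rate of in-hospital major adverse cardiovascular events (MACE) is assumed as 8.4" per cent.
- Size: "96 participating hospitals, 50 patients will be collected in each 6-month cycle in each hospital".
- Roll-out: "the intervention will be started in four steps". Section 3.2.8 adds "Participating hospitals will be randomized to one of four wedges, giving around 24 hospitals per wedge", and Table 2 shows five 6-month periods.
- Clustering: "an intra-class correlation coefficient of 0.10 (data from CPACS-2 study").
- Effect lag: "no delay in the effect of the intervention".

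The result is given as "This study will have 99%, 98% and 85% power to detect relative risk reduction of 25%, 20% and 15% respectively in the primary outcome", repeated in Table 3. The section gives no significance level, formula, scale for the ICC, or correlation between patients of one hospital in different cycles.

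On the analysis, section 4.1 says "GLMM model will be used to evaluate the treatment effect (between intervention groups) and the time effect". The opening of section 4 allows either a GLMM or GEE. Neither place describes the random effects.

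**The concern.** There are two separate problems.

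First, a stepped-wedge power figure is fixed by the number of hospitals, the cell size, the layout, the control rate, the ICC and the test. Section 3.2.10 gives all of these except the test, so Table 3 can be checked. It fails the check at the conventional two-sided 5% level.

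Second, a single ICC treats two patients of one hospital admitted 24 months apart as being as alike as two admitted in the same cycle. The ratio of the between-cycle to the within-cycle correlation is the CAC, and a single ICC sets it to 1. At an ICC of 0.10 the treatment effect is estimated mainly from changes within hospitals, so any hospital-specific fluctuation between cycles adds directly to the error. CAC 1 is the most favourable value, and it is not among the listed assumptions.

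At stake is whether the trial has good power for a 15% reduction, as the protocol tells its readers, or a little better than an even chance. Conditionally, the coverage of the primary interval is also at stake.

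**Working it through.** **Inputs from the protocol.** N = 96 hospitals, 24 per wedge; T = 5 periods; m = 50 per hospital-cycle; p0 = 0.084; ICC = 0.10; no lag. **Assumed:** two-sided alpha 0.05, categorical period effects, normal approximation on the risk-difference scale.

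**Formula.** Standard stepped-wedge variance on cluster-period means (Hussey-Hughes). With s² = p̄(1 − p̄) at the mean of the two rates:

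- a = s²(1 − ICC)/m + s²·ICC·(1 − CAC)
- b = s²·ICC·CAC
- Var = N·a·(a + T·b) / [(N·U − W)·a + (U² + N·T·U − T·W − N·V)·b]
- Power = Φ(δ/SE − 1.96)

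Design constants from Table 2:

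- U = 24 × (4+3+2+1) = 240
- W = 24² + 48² + 72² + 96² = 17,280
- V = 24 × (16+9+4+1) = 720
- N·U − W = 23,040 − 17,280 = 5,760
- Second bracket = 57,600 + 115,200 − 86,400 − 69,120 = 17,280

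**Finding the plan's own figures.** At m = 100 and CAC 1, power is 99.9/98.1/85.0%. At m = 50 with 48 hospitals per wedge it is 99.9/98.2/85.3%. Either set agrees with Table 3 to within a point. Neither is the design in section 3.2.10.

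**Stated inputs, 15% reduction, CAC 1.** p1 = 0.0714, δ = 0.0126, p̄ = 0.0777, s² = 0.07166.

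- a = 0.07166 × 0.9/50 = 0.001290; b = 0.007166
- Numerator = 96 × 0.001290 × (0.001290 + 0.03583) = 0.004597
- Denominator = 5,760 × 0.001290 + 17,280 × 0.007166 = 7.43 + 123.83 = 131.26
- Var = 0.00003502; SE = 0.00592
- δ/SE = 2.13; power = Φ(0.17) = 57%

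| Reduction | δ (points) | SE (points) | δ/SE | Power | Table 3 |
|---|---|---|---|---|---|
| 25% | 2.10 | 0.577 | 3.64 | 95.4% | 99% |
| 20% | 1.68 | 0.584 | 2.87 | 82.0% | 98% |
| 15% | 1.26 | 0.592 | 2.13 | 56.7% | 85% |

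**Could another convention explain Table 3?** A one-sided 5% test gives 97.7/89.1/68.6%. Reading 0.10 as a logit-scale ICC gives a random-intercept variance of (0.10/0.90) × π²/3 = 0.366, which is about 0.03 on the proportion scale, and power of 94.9/81.1/55.7%. Dropping the period effect comes nearest, at 99.95/98.8/88.5% under one variance convention, but it overshoots 85% and contradicts the time effect planned in section 4.1.

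**Decay between cycles (CAC values are assumptions).** The hospital-by-cycle variance moves from b to a. At CAC 0.90 and a 15% reduction, a = 0.001290 + 0.000717 = 0.002007 and b = 0.006450, so SE = 0.00732 and power = Φ(1.72 − 1.96) = 41%.

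| CAC | 25/20/15%, m = 50 | 15%, m = 100 | 15%, m = 50, logit-scale ICC |
|---|---|---|---|
| 1 | 95/82/57 | 85 | 56 |
| 0.99 | 94/80/55 | 81 | 55 |
| 0.95 | 90/72/47 | 67 | 53 |
| 0.90 | 84/64/41 | 55 | 51 |
| 0.80 | 72/52/32 | 40 | 47 |

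**Type I error if only a hospital intercept is fitted.** The true-to-model variance ratio of the effect is 1.26, 1.53 and 2.04 at CAC 0.95, 0.90 and 0.80. Error = 2Φ(−1.96/√ratio) = 8%, 11% and 17%. At CAC 0.99 it is 5.6%. Simulations of 1,000 runs gave 7.5%, 12.0% and 18.9%, against 6.2% at CAC 1. On the logit-scale reading the errors are about 6%, 7% and 8%.

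**The case against.** **The CAC is not in the documents.** This is true. The size of any loss from decay therefore rests on an assumed range, and it is modest if 0.10 is a logit-scale value (about 2.5, 5 and 9 points at CAC 0.95, 0.90 and 0.80). The direction is certain, because every value below 1 lowers power. The mismatch in Table 3 needs no CAC at all.

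**Real cells may exceed 50.** The protocol collects all eligible ACS patients, and section 3.2.1 asks only for more than 40 in 6 months. Cells could be larger, but they could also be smaller: at 40 per cycle, constant-ICC power is 90/73/48%. The stated planning value is 50, and Table 3 must follow from it.

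**Covariance structure belongs in the SAP.** This stands as far as the model goes. A reader might infer that the primary analysis will have an inflated error rate. The protocol does not support that: it leaves the random effects open, allows GEE, and neither includes nor excludes a hospital-by-period term. The error rates above are a conditional risk, and an unseen SAP may already remove it.

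**Two further inferences to avoid.** A reader might take decay as the cause of the gap from 85%, or think that any decay is ruinous. At a 15% reduction, 28 points are lost before any decay, and a CAC of 0.99 costs only 2 to 4 points. Nor do the documents show that 100 patients per cycle were intended; that is only the size that returns the stated figures.

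**Conclusion.** The point holds. Table 3 overstates power for the design in section 3.2.10: about 95/82/57% against 99/98/85%, a shortfall of 28 points at a 15% reduction. This assumes a two-sided 5% test and period effects. None of the alternative conventions shown above yields all three stated figures at 50 patients per cycle and 24 hospitals per wedge.

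As a second and separate layer, constant correlation is an unlisted best case. If 0.10 is on the proportion scale, a CAC of 0.95 to 0.80 takes a further 9 to 25 points at a 15% reduction. The possible type I error of 8% to 17% depends on decay being present and on a hospital-intercept-only model, which the protocol does not specify.

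**What to change.** In section 3.2.10:

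1. Replace Table 3 with power recomputed from the stated inputs, or correct the inputs if 50 per cycle is not what was used.
2. State the alpha and sidedness, the formula, the scale of the 0.10 and the between-period correlation assumed.
3. Show power over CAC 0.8 to 1.0. Section 2.3 describes half-yearly collection in CPACS-2, so a CAC may be estimable from the study that supplied the ICC.

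In section 4.1, as a safeguard, specify a random hospital-by-period effect alongside the random hospital effect and fixed periods, unless the SAP already does so.

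The cost is a less favourable power statement and one extra variance component, with slightly wider intervals if that variance is truly zero. Enrolment does not change.

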3.2 Methods

3.2.1 Inclusion criteria for participating hospitals:

- (1) The time taken to transfer an ACS patient to the nearest tertiary hospital with a cardiac catheter facility is more than 90 minutes;
- (2) The hospital is highly unlikely to have the capacity to perform onsite

percutaneous coronary intervention (PCI) within the next 3 years;

(3) The director or deputy director responsible for medical care is a specialist in internal medicine and is able to set up a QCI team that is participated by directors of the internal medicine department, emergency department, and medical care management department;

(4) Already have established or are able to establish medical records for emergency patients and inpatients, as required by the project;

(5) Able to admit more than 40 ACS patients within 6 months;

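### Table 3 overstates power: under the time-adjusted model of section 4.1 the stated inputs give about 93–95%, 78–82% and 54–57%, not 99%, 98% and 85%

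*Protocol*

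**What the plan says.** Section 3.2.10 and its Table 3 give the power: "This study will have 99%, 98% and 85% power to detect relative risk reduction of 25%, 20% and 15% respectively in the primary outcome". The same section lists these assumptions:

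- Baseline rate: "The baseline incidence rate of in-hospital major adverse cardiovascular events (MACE) is assumed as 8.4" per cent.
- Clustering: "an intra-class correlation coefficient of 0.10 (data from CPACS-2 study".
- Size and steps: "96 participating hospitals, 50 patients will be collected in each 6-month cycle in each hospital, and the intervention will be started in four steps".
- Lag: "no delay in the effect of the intervention".

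Section 3.2.8 gives the layout: "Participating hospitals will be randomized to one of four wedges, giving around 24 hospitals per wedge". Table 2 there shows five six-month periods: one in which all four groups are at baseline, then one group crossing over at the start of each later period.

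Section 4.1 analyses the primary outcome with a generalised linear mixed model that estimates an intervention effect and a time effect. A Cox or logistic model without time is allowed only if neither a time effect nor a time-by-intervention interaction is present.

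The sample-size section does not state the significance level, whether the test is one- or two-sided, or the power formula.

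**The concern.** In a stepped-wedge design the proportion of hospitals on the intervention rises with calendar time. Fitting period effects therefore removes much of the information on the intervention, and power has to be calculated with them in the model. The figures in Table 3 look too high for that model, above all for a 15% reduction.

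This concerns the primary outcome. If the table is wrong, the chance of missing a true 15% reduction is about 43–46% rather than 15%, and of missing a true 20% reduction about 18–22% rather than 2%. Anyone using Table 3 to judge which effects the trial can detect would be misled.

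**Working it through.** **Inputs.** From section 3.2.10: control rate 0.084, ICC 0.10, I = 96 hospitals, m = 50 patients per hospital-period, no lag. From section 3.2.8 and Table 2: T = 5 periods and four groups of 24. Assumed because not stated: significance level 0.05 (two-sided first, then one-sided), equal cluster sizes, no loss of hospitals, and a within-hospital correlation that is constant over periods.

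**Formula.** The Hussey–Hughes variance has a random hospital effect and fixed period effects. X is the 0/1 intervention indicator by hospital and period.

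- U = sum of X = 24 × (4+3+2+1) = 240
- W = sum of squared period totals = 0² + 24² + 48² + 72² + 96² = 17,280
- V = sum of squared hospital totals = 24 × (16+9+4+1) = 720
- Var = I·s²·(s² + T·t²) / [(I·U − W)·s² + (U² + I·T·U − T·W − I·V)·t²]
- I·U − W = 23,040 − 17,280 = 5,760
- U² + I·T·U − T·W − I·V = 57,600 + 115,200 − 86,400 − 69,120 = 17,280

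**Variance taken at the control rate.**

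- Total variance = 0.084 × 0.916 = 0.07694
- t² = 0.10 × 0.07694 = 0.007694
- s² = 0.90 × 0.07694 / 50 = 0.001385
- Var = 96 × 0.001385 × (0.001385 + 5 × 0.007694) / (5,760 × 0.001385 + 17,280 × 0.007694) = 3.76 × 10⁻⁵, so SE = 0.00613

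Power = Φ(difference/SE − 1.96).

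| Relative reduction | Risk difference | z (control-rate variance) | Power | z (mean-rate variance) | Power | Table 3 |
|---|---|---|---|---|---|---|
| 25% | 0.0210 | 3.42 | 93% | 3.64 | 95% | 99% |
| 20% | 0.0168 | 2.74 | 78% | 2.87 | 82% | 98% |
| 15% | 0.0126 | 2.05 | 54% | 2.13 | 57% | 85% |

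The mean-rate columns use the same formula with the variance at the mean of the control and intervention rates (7.35%, 7.56% and 7.77%; SE 0.00577, 0.00584 and 0.00592). A simulated logistic mixed model with period terms (1,500 runs, ICC 0.10 on the latent scale) gave 95%, 79% and 56%.

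**One-sided 0.05.** Replacing 1.96 by 1.645 gives 96–98%, 86–89% and 66–69%.

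**Other ICCs, 15% row, two-sided.** ICC 0 gives 70–73%, 0.01 gives 56–59%, 0.05 gives 53–55% and 0.20 gives 58–61%. No value from 0 to 0.20 comes near 85%.

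**No period effects, 50 patients.** Power is about 100%, 99% and 92–93%. The 15% row is overshot, so this model does not reproduce Table 3 either.

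**What does come close to Table 3.** Each route contradicts a stated input.

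- 100 patients per hospital-period with period effects (mean-rate variance): 99.9%, 98.1% and 85.0%.
- 40 to 41 patients without period effects (control-rate variance): 99.9%, 97.8–98.1% and 84.7–85.5%.
- 50 patients without period effects, at the CPACS-2 rate of 7.6%, with the full rather than the within-hospital variance for each patient: 99.9%, 97.9% and 84.9%.

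**Detectable reduction, two-sided 0.05, 80% power.** With control-rate variance, (1.960 + 0.842) × 0.00613 / 0.084 = 20.4%. Mean-rate variance gives about 19.5%.

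**The case against.** Four points can be made for the plan.

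*The significance level is not given, so the power cannot be said to be wrong.* It is true that the inputs are incomplete, and any replacement figure must declare its assumption. But one-sided 0.05 leaves the 15% row at 66–69%. Even with the variance at the intervention rate, the most favourable convention tried, it reaches only 71.5%.

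*Section 4.1 also names a model without time.* A reader might infer that Table 3 is out of reach under every model in the protocol. That is too strong: without period effects, power at 50 patients is above every row of the table. But that model depends on what the data show and cannot be the planning basis, and it does not yield the printed figures.

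*The recalculated figures depend on convention.* This stands. They move by 2–4 points with the variance used, so a single triple such as 93/78/54 would be too precise. Whether the 20% row lies just under or just over 80% cannot be settled. The 25% row, at 93–95%, remains adequate.

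*Hospital criterion (5) in section 3.2.1.* It reads "Able to admit more than 40 ACS patients within 6 months", and a reader might infer a conflict with the 50 patients assumed. The documents do not support that. The criterion is an eligibility floor, and a floor just above 40 is compatible with an average of 50.

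It is also tempting to conclude that the table was run with twice the stated cluster-period size. The match at 100 patients is suggestive, but about 40 without period effects fits nearly as well, and the protocol does not say how the figures were obtained.

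**Conclusion.** The point holds in this form: the stated inputs, analysed with the first-line model of section 4.1, do not deliver the power in Table 3. At an assumed two-sided 0.05 the 20% row is overstated by about 16–20 points (98% against 78–82%) and the 15% row by about 28–31 points (85% against 54–57%). The 25% row is overstated by about 4–6 points, which matters little.

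The result rests on equal cluster sizes, no loss of hospitals and a constant within-hospital correlation. The last is favourable to the plan: with an assumed cluster autocorrelation of 0.9, power would be about 84%, 64% and 41% (mean-rate variance).

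This does not show that the trial needs more patients or that its design is unsound. It shows that the protocol claims a sensitivity to a 15% reduction that its own design does not have.

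**What to change.** In section 3.2.10, recalculate Table 3 and the sentence above it for the section 4.1 model, with a hospital random effect and period effects. State the significance level, sidedness, variance convention and number of patients per hospital-period used. With the current inputs and two-sided 0.05 the figures become about 93–95%, 78–82% and 54–57%; the final table should give one convention and name it. Add the detectable reduction, about 20% at 80% power, and withdraw the claim of 85% power for a 15% reduction. If the sponsor's original calculation used a different cluster-period size or left out period effects, the protocol should say so and reconcile it with the stated inputs.

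The cost is one table and a few sentences. No extra patients and no change to hospital criterion (5) are needed. The only downside is a less favourable stated power.

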3.3 Quality control

Each hospital will receive training of the research protocol before the start of the project and will receive the training on intervention protocol before the commencement of the intervention.

After the research protocol training but prior to the formal data entry a period of one month is blocked for practice. During this period, the data entry staff will be checked if he/she is qualified by examining whether the data inputted into the CPACS-3 IT system are matched with the medical charts separately sent to the coordinating center. After the qualification validated, the participating hospital could begin its formal recruitment.

Each participating hospital will receive the site monitoring visit at least twice, one within half a year after initiating the study and one within the last year before the end of the study. There is no difference in the time of the first monitoring visits. In the first six months of the project (February-June), the first monitoring visits of all 96 centers will be completed; the second monitoring visits will be done in 2-3 times. 20% to 40% of 96 centers will be checked at each time, and the second monitoring visits will be completed within one and a half years. Routine data queries will be conducted through the data management center.

The site monitoring visits should check the establishment and operation of the QCI team, documentation and filing, patient ID verification, original data sourcing, the implementation of clinical pathway, etc.

The site monitoring results will be reported back to the hospital QCI team as well as the project team, the corresponding local health bureaus and the Ministry of Health. The project team may raise critics and appraisals to the participating hospital on the basis of the monitoring results. The project team can withdraw hospitals that are seriously unqualified for data authenticity and data quality.

4. Statistical analysis plan

As the stepped-wedge cluster randomized trial design, we plan to analyse the study data at individual level. Considering that the response variables may be non-normal distribution or binomial distribution, and the sizes of the clusters may be unequal, we plan to use the generalized linear mixed models (GLMM) or generalized estimating equations (GEE) to do statistical analyses.

4.1 Effectiveness evaluation

For the primary end point (binary variable, in hospital major adverse cardiovascular events (MACE), including stroke, AMI, hospital readmission, vascular reconstruction and all-cause mortality), GLMM model will be used to evaluate the treatment effect (between intervention groups) and the time effect (between different patients in different time periods), with LOGIT/POSSION conversion of the end point. If there is neither the time effect nor the interaction term between time and intervention, the COX model or LOGISTIC regression model will be used to estimate the intervention effect after adjustment of covariates.

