Between 2005 and 2010, we conducted a trial (CPACS-2) in 15,000 patients admitted to 75 hospitals (from 17 provinces) throughout China to determine whether the routine use of a quality improvement initiative, could increase evidence-based management of ACS. The trial showed that although the intervention could improve certain aspects of care (for example, the appropriate prescription of recommended therapies at discharge increased from 51.2% to 61.6% (OR 1.42; 95% CI: 1.00 to 2.02; p=0.061)), major system-level barriers including a lack of top down support, prevented universal improvement. Most patients with ACS in China present to non-tertiary hospitals in poorer areas, where the financial burden of ACS is catastrophic. However, relatively few of these hospitals were included in the CPACS-2. Furthermore the study was not powered to measure the impact of the intervention

on clinical outcomes such as in-hospital mortality. As a result, the social and economic benefits of the intervention remain unclear.

This study, Clinical Pathways for the management of Acute Coronary Syndromes – Phase 3 (CPACS-3), aims to determine the effectiveness and cost-effectiveness of a complex, quality improvement initiative in 96 non-tertiary, non-PCI hospitals throughout China in reducing the risk of major adverse cardiovascular events in patients admitted with ACS.

2. Background

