recommend four drugs (aspirin, beta-blockers, ACEI/ARB and statin) was 61.6% and 51.2% respectively (OR 1.42; 95% CI: 1.00-2.02; $p=0.061$); with the implementation of intervention, the hospital stay was significantly reduced ($p=0.001$) and the proportion of patients treated with the four drugs also significantly increased ($p=0.004$). Other indicators, such as the proportion of STEMI with reperfusion therapy, the door-to-needle time and door-to-balloon time also showed a trend of improvement, but not statistically significant. The incidence of major adverse events (including death, myocardial infarction, and stroke) in the hospital decreased, but which was only significant before controlling potential confounders ($p=0.009$).

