3.2.5 Data collection

Data to be collected at discharge:

From the beginning of the study, all clinical data will be collected for all discharged or deceased patients who was diagnosed as acute coronary syndrome in the emergency department and inpatient department. Data to be collected include demography, clinical manifestations, the medical treatments at the emergency room, during hospital stay, and at discharge, as well as adverse events during hospitalization, and prognosis (basic questionnaire, appendix 1), costs during hospitalization (appendix 2) and the patients' quality of life (appendix 3). At the same time, the mobile phone numbers of patients or their families are registered for

conducting the patient satisfaction survey through the SMS platform (patient satisfaction survey questionnaire, appendix 4).

Data to be collected at follow-ups:

Patients who are alive at discharge and sign the informed consent will be followed up twice (at 6 months and 12 months). Data collection at follow-ups includes lifestyle, medical treatments, rehabilitation, adverse events (myocardial infarction, stroke, revascularization, hospitalization and death) (follow-up questionnaire, appendix 5). A quality of life survey will be conducted at the second follow-up visit (QoL35, appendix 3).

Data collectors:

The information at discharge and follow-ups (appendix 2, appendix 3 and appendix 5) and the informed consent to patients should be completed by the medical doctor in the department who is trained and assigned the responsibility specifically.

Data entry staff:

[figure not shown]
The entry of data (appendix 1, appendix 2, appendix 3, appendix 5) shall be completed by an independent staff at medical fair management office who are not responsible for medical diagnosis and treatment.

Data collection process:

Data collectors complete the appendix 2 and 3 on the day or one day before the patient's discharge, check the address and valid phone numbers, get informed consent for follow-up, make the appointment for follow-up time, as well as inform the data entry staff to enter the patient's medical records and questionnaires into the CPACS-3 IT system. All the patients' data should be entered within 2 weeks.

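### The in-hospital primary end point has three components in section 3.2.9 and five in section 4.1; one added component cannot occur in the index stay, and the 8.4% planning rate is tied to neither list

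*Protocol*

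**What the plan says.** The protocol describes its single primary end point twice.

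- Section 3.2.9 (Outcomes): "in-hospital major adverse cardiovascular events (MACE) comprising all-cause mortality, myocardial infarction or re-infarction and stroke".
- Section 4.1 (Effectiveness evaluation): "in hospital major adverse cardiovascular events (MACE), including stroke, AMI, hospital readmission, vascular reconstruction and all-cause mortality".

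Three other places bear on the difference.

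- Section 3.2.5 (Data collection) lists what is recorded at the 6- and 12-month follow-up: "adverse events (myocardial infarction, stroke, revascularization, hospitalization and death". Follow-up is restricted to patients who leave hospital alive and sign consent.
- Section 2.3 reports on the preceding trial: "The incidence of major adverse events (including death, myocardial infarction, and stroke) in the hospital decreased".
- Section 3.2.10 (Sample Size) sets the planning rate at 8.4%, the CPACS-1 figure, and gives 7.6% for CPACS-2. It labels the rate only as in-hospital MACE and names no components.

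**The concern.** A confirmatory trial needs one definition of its primary end point. Here the outcome section and the analysis section give different lists, and the protocol states no order of precedence. Two analysts could each follow the protocol and test different end points, and the choice could be made after the data are seen.

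The longer list also conflicts with its own label. It keeps the restriction to events in hospital but adds readmission, which can only follow a discharge. An analyst who tries to make sense of it is drawn towards the follow-up data, where such events are recorded. That would change who contributes to the end point and, in a stepped-wedge design, when events are counted relative to the hospital's crossover.

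**Working it through.** **1. The lists side by side.**

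| Event | 3.2.9, primary outcome | 4.1, primary end point | 3.2.5, follow-up | 2.3, CPACS-2 in hospital |
|---|---|---|---|---|
| Death | yes | yes | yes | yes |
| Myocardial infarction | yes (or re-infarction) | yes | yes | yes |
| Stroke | yes | yes | yes | yes |
| Readmission / hospitalisation | no | yes | yes | no |
| Revascularisation | no | yes | yes | no |

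The wording in 3.2.9 makes a closed list of three. The list in 4.1 has five. It matches the follow-up list in kind, while 3.2.9 matches the CPACS-2 in-hospital events. That 4.1 was carried over from the follow-up list is an inference; the protocol does not say so.

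**2. Do the two added items fit an in-hospital end point?** Readmission does not, by definition. Revascularisation is not strictly impossible, for example after transfer. But the Overview describes a "quality improvement initiative in 96 non-tertiary, non-PCI hospitals throughout China", and hospital criterion 2 in section 3.2.1 selects sites where on-site PCI is very unlikely for the next 3 years. It is therefore not expected on site.

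**3. Who would contribute if the items came from follow-up?** In-hospital data come from the charts of all eligible patients without consent (sections 3.2.5 and 8). Follow-up data exist only for consenting survivors. A composite of the two would have different ascertainment for its different parts.

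**4. When would the events fall?** Table 2 has 10 control cells: A0; B0, B1; C0, C1, C2; D0, D1, D2, D3. Each period lasts 6 months.

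- A 6-month visit falls one period later. The hospital is then under intervention for patients from A0, B1, C2 and D3: 4 of 10 cells.
- A 12-month visit falls two periods later. The hospital is then under intervention for patients from A0, B0, B1, C1, C2, D2 and D3: 7 of 10 cells.

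Follow-up of control-period patients could thus run into intervention periods. An end point confined to the index stay largely avoids this.

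**5. What would it do to power?** The stated power is 99%, 98% and 85% for relative reductions of 25%, 20% and 15%.

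Inputs from 3.2.10 and Table 2: I = 96 hospitals, m = 50 per hospital and period, T = 5 periods, ICC 0.10, rate 8.4%. Two-sided alpha 0.05 is assumed, since none is stated. For a stepped wedge with period effects and a random hospital effect (Hussey-Hughes):

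Var = Iσ²(σ² + Tτ²) / [(IU − W)σ² + (U² + ITU − TW − IV)τ²],

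with τ² = 0.10v, σ² = 0.90v/50 and v the binomial variance at the mean of the two rates. The design sums are:

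- U = 24 × (4+3+2+1) = 240
- W = 24² + 48² + 72² + 96² = 17,280
- V = 24 × (16+9+4+1) = 720

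For a 15% reduction:

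- The rates are 0.084 and 0.0714, so v = 0.0777 × 0.9223 = 0.0717.
- The standard error is 0.00592.
- z = 0.0126/0.00592 − 1.96 = 0.17, so power is 57%.

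For 25%, 20% and 15% the results are 95%, 82% and 57%. The stated figures are not reproduced. That is a separate matter, and the formula serves here only to compare definitions on one footing.

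The documents give no five-component rate, so a total of 10% to 15% is assumed:

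| Assumed total rate | Whole composite falls by 25/20/15% | Added events unaffected by the intervention |
|---|---|---|
| 8.4% (three components) | 95 / 82 / 57% | 95 / 82 / 57% |
| 10% | 98 / 89 / 65% | 91 / 75 / 50% |
| 15% | 99.9 / 98 / 84% | 78 / 59 / 37% |

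Power can move either way. The table holds 50 per cell and ICC 0.10 fixed, and it applies only if follow-up events are counted.

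**The case against.** Section 4.1 keeps the restriction to hospital events. Read literally, readmission then adds nothing and revascularisation adds little, so the five-item end point would nearly equal the three-item one. This stands, and it limits the consequences: the mixing of populations and periods arises only if an analyst goes to follow-up data. It does not make the two definitions agree. A statistical analysis plan that is not shown may settle the matter, but the protocol would still contradict itself.

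Two stronger readings are tempting and are not supported.

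- A reader might infer that the intervention would increase referral for revascularisation, so that 4.1 would count good care as harm and cancel a stated share of the effect. No component in section 3.2.7 mentions referral or transfer, the reperfusion indicators in Table 1 concern fibrinolysis, and section 3 describes the hospitals as too distant to transfer patients. Any figure for a cancelled effect would rest on an assumed increase in events that the documents do not supply.
- A reader might infer that the trial was powered on the three-component definition. The 8.4% comes from CPACS-1, and the protocol nowhere gives the components used there. Section 2.3 names three for CPACS-2 but does not tie them to the 7.6%. The rate has no stated component basis under either definition.

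**Conclusion.** The contradiction stands and must be corrected before analysis, because it concerns the primary end point. Sections 3.2.9 and 4.1 give three and five components for the same in-hospital outcome, and 4.1 is wrong as written because readmission cannot occur during the index stay. This rests on the text alone and needs no assumption.

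The size of the consequence depends on how 4.1 is read. Taken literally, few or no events are added. Taken from follow-up, the end point changes its population and its timing, and the effect on power is undetermined in direction. No bias or loss of effect can be quantified from the protocol. It is also unsettled which definition the 8.4% refers to.

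**What to change.** 1. In section 4.1, replace the bracketed list with the 3.2.9 definition: in-hospital all-cause death, myocardial infarction or re-infarction, or stroke. Remove readmission and vascular reconstruction from the primary end point.
2. In section 3.2.10, confirm that the 8.4% refers to these three components. If it does not, give the rate that does and recompute power.

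Readmission and revascularisation are already collected at follow-up and may be reported separately; this is optional and not needed to correct the error. The cost is one sentence in 4.1 and a check of the CPACS-1 definition for 3.2.10, with no change to data collection.
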